7.14 Compliance/Adherence

In select cases, the Investigator may need to discuss with the patient whether they should continue the study and make relevant explanations in certain situations, including but not limited to the following:

- 1) The Investigator considers it advisable for the patient to stop the study from the perspective of medical ethics, or believes that withdrawal from the study may be in the best interest of the patient.
- 2) During the study, the patient does not comply with the study plan and shows poor compliance (eg, failure to take the study drug or failure to obtain samples for PK and safety evaluation as required by the protocol).
- 3) The patient evidences behavioral issues during the study that may affect study assessments

7.15 Randomization and Blinding

The study will not be randomized and will be unblinded.

V4.0_8 Jul 2024 Page 49 of 68

8 STUDY POPULATION

8.1 Inclusion Criteria

Patients must meet the following criteria for study entry:

- 1) In the opinion of the Investigator, the patient is capable of understanding and complying with protocol requirements.
- 2) The patient signs and dates a written ICF prior to the initiation of any study procedures.
- 3) The patient has a diagnosis of AD (according to the criteria established by Hanifin and Rajka, 1980). The diagnosis of AD must have been present for at least 6 months.
- 4) The patient is aged 18 to 65 years, inclusive at the time of consent. Patients of any gender are eligible.
- 5) A female patient weighs at least 45 kg and a male patient weighs at least 50 kg. The patient has a BMI between 18.0 and 32.0 kg/m² inclusive at Screening.
- 6) The EASI is \geq 12 at Screening and on Day 1.
- 7) The score on the IGA is ≥ 3 (scale of 0 to 4) at Screening and on Day 1.
- 8) The total body surface area (BSA) affected by AD is $\geq 10\%$ as assessed by the physical examination at Screening and on Day 1.
- 9) The patient has:
 - (a) not received prior treatment with topical or systemic medications OR
 - (b) the patient has active disease despite topical or systemic treatment as per the Investigator at the time of screening.
 - Prescription moisturizers or moisturizers containing additives such as ceramide, hyaluronic acid, urea, or filaggrin degradation products can be allowed if the patient agrees to continue using at the current dose during the study.
- 10) A male patient who is non-sterilized and sexually active with a female partner of childbearing potential agrees to use highly effective contraception from the time of signing the ICF throughout the duration of the study treatment and for 90 days (~5 half-lives) after the last dose of study drug (See Section 8.3).
- 11) A female patient of childbearing potential who is sexually active with a non-sterilized male partner agrees to use highly effective contraception from the time of signing the ICF throughout the duration of the study treatment and for 90 days after the last dose of study drug (See Section 8.3).
- 12) The patient has a negative urine/blood result for drugs of abuse (if there are concerns in the opinion of the Investigators regarding the use of illicit drugs, including cannabinoid products).

8.2 Exclusion Criteria

Any patient who meets any of the following criteria will be excluded from the study:

V4.0_8 Jul 2024 Page 50 of 68

1) The patient has received any of the following treatments but did not finish the required washout period as stated in the following table. After the washout period, the patients can be considered for study treatment.

Therapy	Washout Duration Required before First Dose of BSI-045B
Tralokinumab	12 weeks
Dupilumab	12 weeks
Phototherapy	4 weeks
Abrocitinib	4 weeks
Upadacitinib	4 weeks
Topical corticosteroids	1 week
Topical calcineurin inhibitors	1 week
Investigational Products	4 weeks
All Other Therapies prescribed for	3 weeks or 4 half-lives, whichever is longer
therapeutic immunosuppression or	
immunomodulation	

- 2) The patient has another dermatologic condition that might confound a diagnosis of AD or a treatment assessment.
- 3) The patient has any clinically significant illness that may affect the safety, increase the risk for seizure or lower the seizure threshold, or potentially confound the study results, such as cardiovascular, neurologic, pulmonary, hepatic, renal, metabolic, gastrointestinal, immunologic, endocrine, or psychiatric disease or disorder, or other abnormality. It is the responsibility of the Investigator to assess the clinical significance of a patient's condition; however, consultation with the Sponsor's Medical Monitor may be warranted.
- 4) The patient has abnormal laboratory values during the Screening Period: ALT and/or AST > 1.5 times the upper limit of normal (ULN), total bilirubin \geq 1.5 mg/dL, estimated glomerular filtration rate (GFR) < 60 mL/min (based on Cockcroft-Gault calculation), hemoglobin (Hgb) \leq 10 g/dL, platelet count \leq 150 \times 10³/ μ L. Individual exceptions may be granted with the agreement of the Sponsor and the Investigator.
- 5) The patient has a history of anaphylaxis following biologic therapy.
- 6) The patient has a history of allergy to corticosteroids, diphenhydramine, hydroxyzine, cetirizine, or fexofenadine.
- 7) The patient has a history of a clinically significant infection within 4 weeks prior to Screening.
- 8) The patient has been diagnosed with a helminthic parasitic infection within 6 months prior to Screening.
- 9) The patient has a history of drug abuse (defined as any illicit drug use) or a history of alcohol abuse within 1 year prior to Screening or is unwilling to agree to abstain from excessive alcohol consumption and drugs (including cannabinoids) throughout the study.
- 10) The patient had a major surgical or major dental procedure within 8 weeks prior to Screening.

V4.0_8 Jul 2024 Page 51 of 68

11) The patient is pregnant or lactating or intends to donate ova before, during, or within 90 days (~ 5 half-lives) since the last dose of study drug.

- 12) If male, the patient intends to donate sperm during this study or within 90 days (~ 5 half-lives) since the last dose of study drug.
- 13) The patient has a history of neurologic abnormalities including abnormal electroencephalography, brain injury including traumatic injury, perinatal cerebropathy, postnatal brain damage, blood-brain barrier abnormality, and cavernous angioma.
- 14) The patient has a history of cerebral arteriosclerosis.
- 15) The patient has a history of cancer, except for adequately treated basal or squamous cell skin cancer or in situ cancers; or any other cancer from which the patient has been disease-free for at least 5 years prior to the first dose of study drug.
- 16) The patient has a positive test result for HbsAg, anti-HCV, a history of active tuberculosis, a positive test result for HIV, or a known history of HIV infection at Screening.
- 17) The patient has poor peripheral venous access.
- 18) The patient has donated or lost \geq 450 mL of blood (including plasmapheresis) or had a transfusion of any blood product within 90 days prior to the first dose of study drug.
- 19) The patient has an abnormal (clinically significant) ECG at Screening and/or on Day1. Entry of any patient with an abnormal (not clinically significant) ECG must be approved and documented by signature of the Investigator. In the case of a corrected QT interval (Fridericia) (QTcF) > 450 ms or > 470 ms (patients with bundle branch block) or PR interval outside the range of 115 to 220 ms, assessment may be repeated once for eligibility determination at Screening and/or on Day1.
- 20) The patient has poorly controlled hypertension and is not considered suitable for participation in this study in the judgement of the Investigators at Screening and/or on Day1.
- 21) The patient has abnormal resting heart rate and is not considered suitable for participation in this study in the judgement of the Investigator at Screening and/or on Day1. Assessment is allowed to be repeated once for eligibility determination at Screening and/or on Day1 if deemed necessary.
- 22) The patient plans to use any other prohibited medication or undergo any prohibited procedure during the study. Oral antibiotics are permitted. Bleach baths are not permitted.
- 23) The patient has a risk of suicide on the Patient Health Questionnaire-2 (PH-2) or in the judgment of the Investigator, or the patient has made a suicide attempt or has a history of deliberate self-harm within 6 months prior to Screening.
- 24) The patient is compulsorily detained for a medical or psychiatric illness.
- 25) The patient or their immediate family are personnel at the study site.

V4.0_8 Jul 2024 Page 52 of 68

26) The patient is unable to comply with restrictions and prohibited activities/treatments as listed in the study protocol.

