AD = atopic dermatitis; AE = adverse event; ALT = alanine aminotransferase; aPTT = activated partial thromboplastin time; AST = aspartate aminotransferase; CCL-17 = C-C chemokine ligand 17; D = day; EASI = Eczema and Severity Index; ECG = electrocardiography; GGT = gamma glutamyl transferase; HbsAg = hepatitis B surface antigen; HBV = hepatitis B virus; HCV = hepatitis C virus; HIV = human immunodeficiency virus; ICF = Informed Consent Form; IGA = Investigator's Global Assessment; IgE = immunoglobulin E; IL = interleukin; INR = international normalized ratio; LDH = lactate dehydrogenase; PD = pharmacodynamic; PH-2 = Patient Health Questionnaire-2; PK = pharmacokinetic; PP-NRS = Peak Pruritus Numerical Rating Scale; PT = prothrombin time; Q2W = every 2 weeks; QW = every week; RBC = red blood cell; SC = subcutaneous; TARC = thymus and activation regulated chemokine; W = week; WBC = white blood cell.

- 1. Screening duration varies by prior AD treatment and the Investigator should consult Section 7.2 for required washout duration. For patients not requiring washout, screening assessments should be conducted after ICF been signed and the screening period will take up to 2 weeks; once they complete their screening assessments and meet all study inclusions/exclusions, the patients will advance directly to W1D1. For patients requiring washout, screening assessments should be conducted after ICF been signed, if all inclusion/exclusions are met, they will be notified by the study sites to start the washout for prior AD treatment. Screening assessments should be repeated if they are performed ≥14 days before W1D1.
- 2. W1D1 pre-dosing is set to confirm the eligibility of patients.
- 3. BSI-045B administration after W4 (4 loading doses) at Q2W interval to Week 24.

V4.0_8 Jul 2024 Page 18 of 68

- 4. Order of assessments: When collecting PK, immunogenicity, biomarker, and clinical laboratory samples, vital signs, and/or ECG assessments are scheduled to occur at the same time point, ECG and vital signs testing will be performed prior to blood collections. The preferred order of assessments is: 1) ECG, 2) vital signs, 3) PK, immunogenicity, and biomarker sampling, 4) clinical laboratory sampling.
- 5. Height and weight, and BSA affected by AD should be determined at the Screening physical examination. BSA affected by AD should also be determined at W1D1 pre-dosing. Symptom-driven examinations will be performed at other time points beyond screening.

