7.2 Washout Period

Patients will start with a washout period for anti-AD treatment prior to study treatment, including systemic and topical agents and phototherapy. The duration of the washout period varies by therapy and the Investigator should consult Table 6. Eligible patients who complete the washout period for previous therapies for AD will be treated with BSI-045B.

Washout period is required for patients already on treatment for AD. Washout duration requirements is described in Table 6.

Table 6. Washout Durations Required Before Initial Dose of BSI-045B, by Therapy

Therapy	Washout Duration Required before First Dose of BSI-045B
Tralokinumab	12 weeks
Dupilumab	12 weeks
Phototherapy	4 weeks
Abrocitinib	4 weeks
Upadacitinib	4 weeks
Topical corticosteroids	1 week
Topical calcineurin inhibitors	1 week
Investigational Products	4 weeks
All Other Therapies prescribed for therapeutic	3 weeks or 4 half-lives, whichever is
immunosuppression or immunomodulation	longer

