7.9.2 Assessments at Screening

Screening assessments will be performed after the patients signed the ICF. After all screening results are obtained, eligible patients who require no washout will be enrolled to the study directly; eligible patients who require washout will start washout and repeat some screening assessments during Day-14 to Day-1.

Rescreening is allowed after a delay of at least 4 weeks from the initial screening assessment. Any rescreening should be approved by the Sponsor.

A complete history will be recorded at Screening and will include medical history, surgical history, smoking history, alcohol use history, drug abuse history, prior and current medication, blood donation history, allergy history, and other demographic information.

Physical examinations at Screening will include weight, height, and body mass index (BMI), as well as a complete examination. Symptom-driven examinations will be performed at other time points.

Other screening assessments will include 12-lead ECG, blood pregnancy test (females of childbearing potential only), and vital signs (blood pressure, pulse, temperature, and

V4.0_8 Jul 2024 Page 42 of 68

respiratory rate). A subset of these tests will be completed at other time points, as detailed in the Schedule of Activities.

A screening for drugs of abuse is optional (per the discretion of the Investigator).

Clinical laboratory assessments at Screening will include those listed in Table 7 and will be conducted as site policy requires.

Table 7. Clinical Laboratory Assessments, BSI-045B-002

Type of Test	Laboratory Parameters
Hematology	Hemoglobin, hematocrit, WBC count and differential, RBC count and indices, platelet count
Chemistry	Sodium, potassium, chloride, bicarbonate, calcium, phosphorus, magnesium, glucose, BUN, creatinine, uric acid, ALT, AST, GGT, alkaline phosphatase, total protein, albumin, globulin, total bilirubin, LDH, total cholesterol, triglycerides
Coagulation	PT, aPTT, fibrinogen, INR
Virology (performed only at Screening)	HbsAg, anti-HCV, HIV
Urinalysis	Protein, glucose, ketones, occult blood, urobilinogen, urine sediment microscopy (if other parameters abnormal)

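### Exclusions 7, 8 and the self-harm limb of 23 look back from Screening, so events during a washout of up to 12 weeks or longer need not exclude the patient

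*Protocol*

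**What the plan says.** Three exclusions in Protocol Section 8.2, repeated in the Synopsis, count back from Screening:

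- Exclusion 7: "The patient has a history of a clinically significant infection within 4 weeks prior to Screening".
- Exclusion 8: "The patient has been diagnosed with a helminthic parasitic infection within 6 months prior to Screening".
- Exclusion 23, second limb: a suicide attempt or "history of deliberate self-harm within 6 months prior to Screening". Its first limb has no window: "The patient has a risk of suicide on the Patient Health Questionnaire-2 (PH-2) or in the judgment of the Investigator".

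Other criteria use a later anchor. Exclusion 18 covers a patient who "had a transfusion of any blood product within 90 days prior to the first dose of study drug", and exclusion 15 (cancer history) also counts from first dose. Inclusions 6 to 8 and exclusions 19 to 21 name Day 1 as well as Screening.

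On timing, Table 1 footnote 1 has washout patients screened first and, if eligible, told to start washout. The longest fixed washout in Section 7.2 is 12 weeks, for tralokinumab and dupilumab (the table row reads "Dupilumab 12 weeks"). Other immunomodulators need 3 weeks or 4 half-lives, whichever is longer.

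On repetition, footnote 1 says "Screening assessments should be repeated if they are performed ≥14 days before W1D1", while Section 7.9.2 says "eligible patients who require washout will start washout and repeat some screening assessments during Day-14 to Day-1". Footnote 7 names only clinical laboratory tests and urine toxicology. Table 1 marks medical history and the PH-2 at Screening only. The eligibility criteria are marked at Screening and again before dosing on W1D1, which footnote 2 says is there to confirm eligibility.

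**The concern.** A look-back window is meant to describe the patient's state at the start of exposure. Here it ends at a visit that can fall weeks or months before exposure. A clinically significant infection treated and cleared in washout week 11, or a helminth diagnosis made and treated in week 6, happened after Screening and so lies outside the written window. Checking the same sentence again on W1D1 gives the same answer.

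The stake is patient protection and consistent application across sites. Protocol Section 5.2.1 describes TSLP as a regulator of type 2 responses at mucosal barriers, which makes recent infection and helminth exposure relevant when an anti-TSLP antibody is started. That link is an inference, because the protocol gives no reason for these exclusions, and it does not extend to self-harm. In a multicenter study, sites may also read *Screening* differently for a patient who has been screened twice.

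**Working it through.** The plan states no figure on this point, so there is none to reproduce. The check is a day count.

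**Inputs.** Infection window 28 days (exclusion 7). Washouts of 1, 3, 4 and 12 weeks (Section 7.2; 3 weeks is the minimum for other immunomodulators). Screening of up to 2 weeks for patients without washout (footnote 1). Repeat screening on Day -14 to Day -1 (Section 7.9.2).

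**Assumptions.** The prior therapy is stopped only when the site gives notice to start washout. Screening before washout takes 0 to 14 days; the documents give the two-week figure only for patients without washout.

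**Formulas.** Gap g = 7 × washout weeks + screening days before washout. Exclusion 7 covers from g + 28 to g days before first dose. The last g days are uncovered. Of the final 28 days, max(0, 28 − g) are covered.

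| Case | Gap g (days) | Exclusion 7 covers (days before first dose) | Days covered of the last 28 |
|---|---|---|---|
| 12-week washout | 84 to 98 | 112–84 to 126–98 | 0 |
| 4-week washout | 28 to 42 | 56–28 to 70–42 | 0 |
| 3-week washout | 21 to 35 | 49–21 to 63–35 | 7 to 0 |
| 1-week washout | 7 to 21 | 35–7 to 49–21 | 21 to 7 |
| No washout | up to 14 | 42–14 at the longest | at least 14 |
| Repeat screening counts as Screening | 1 to 14 | 29–1 to 42–14 | 27 to 14 |

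The 4-half-life rule gives a washout beyond 12 weeks once the half-life exceeds 84 / 4 = 21 days.

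For exclusion 8 and the self-harm limb of 23, take six months as 26 × 7 = 182 days (an assumption). With a gap of 84 to 98 days, 84/182 = 46% to 98/182 = 54% of the six months before first dose is uncovered. That is the half nearest to dosing.

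**Which date is Screening?** Footnote 1 says the duration of screening varies with prior treatment, which makes it a period that includes washout. A window ending before Screening then most naturally ends where that period begins. No passage says that a repeated assessment moves the date.

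**Do other rules bridge the interval?** Two other exclusions that refer to Screening have a bridge: exclusion 9 (drug and alcohol abuse) also requires abstention during the study, and exclusion 10 (surgery) is backed by the prohibition in Section 9.5. Exclusions 7 and 8 and the self-harm limb of 23 have no such bridge. Adverse events are recorded from consent (Section 10.5), so an infection during washout would be on file, but no rule makes it exclusionary.

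**The case against.** The strongest reply is that the protocol does look again before dosing. Footnote 1, taken alone, repeats every screening assessment done 14 or more days before W1D1. Medical history and the PH-2 are screening assessments, so both would be refreshed. If that repeat also resets the Screening date, the gap falls to 1 to 14 days. This stands as one possible reading. However, Section 7.9.2, footnote 7 and the Screening-only marks in Table 1 point to a narrower repeat, and even the generous reading leaves up to half of the 28-day infection window open.

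A reader might infer that events just before dosing can never exclude the patient. The documents do not support that. Exclusion 3 (clinically significant illness) and the first limb of exclusion 23 have no window and rest on investigator judgment. An active helminth infection on Day 1, or self-harm during washout, can be caught there. Exclusion 3 is a weaker route for an illness that has resolved, because it concerns an illness the patient has.

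A reader might also infer that early infections would be miscounted as treatment-emergent. That does not follow. Under Protocol Section 11.5 and SAP Section 4.8.2, an infection that began in washout and continues unchanged is not a TEAE, and a new infection after dosing is a TEAE whatever anchor exclusion 7 uses.

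Finally, 12 weeks is the long case. Washout runs back from first dose, so a biologic stopped before Screening shortens the gap. The documents do not say how many of the 20 to 24 evaluable patients will need a 12-week washout, and it may be none.

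**Conclusion.** The point holds as a gap in the eligibility wording. Read literally, exclusions 7 and 8 and the self-harm limb of 23 do not reach events between Screening and first dose, and the W1D1 check cannot cure this because it applies the same text. The uncovered interval is 12 to 14 weeks for a patient still on dupilumab or tralokinumab at Screening; the upper figure assumes two weeks of screening before washout. It can be longer under the 4-half-life rule and is shorter for the other fixed washouts or where the therapy was stopped earlier. It is at most 14 days for patients without washout or if repeat screening resets the date.

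After allowing for investigator judgment, the clearest remaining gap is an infection or helminth diagnosis that has resolved before Day 1. The sample size, the endpoints and the TEAE definition are unaffected. This is a cheap safety improvement that should be made.

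**What to change.** In Section 8.2 and the Synopsis, anchor the look-backs in exclusions 7, 8 and the self-harm limb of 23 to the first dose of study drug, as exclusions 15 and 18 already are. Keep the stated durations, and check them at the existing W1D1 eligibility confirmation, covering events since Screening. Merely defining Screening as the repeat visit would be weaker, since up to 14 days would stay open.

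Separately, reconcile four places so that it is clear which assessments are repeated after washout: Table 1 footnote 1, Section 7.9.2, footnote 7, and the Screening-only marks for medical history and the PH-2.

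The cost is a protocol wording change with no added visit. Adverse events and concomitant medications are already recorded from consent, so the information is at hand. The downside is that a few patients with an event during washout will be deferred or excluded.

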8.3 Contraception Requirements

Women of childbearing potential must use a highly effective method of contraception from the time of giving informed consent until at least 90 days after the last dose of study drug. Women are considered to be of childbearing potential following menarche until becoming postmenopausal (defined as no menses for at least 12 months without an alternative medical cause) unless permanently sterile. A high follicle-stimulating hormone (FSH) level in the postmenopausal range may be used to confirm a postmenopausal state in women not using hormonal contraception or hormonal replacement therapy. However, in the absence of 12 months of amenorrhea, a single FSH measurement is insufficient. Permanent sterilization methods include hysterectomy, bilateral salpingectomy, and bilateral oophorectomy.

Males with partners who are females of reproductive potential must agree to use condoms, and their partners will use a highly effective contraceptive method from the time of informed consent and for 90 days after the last dose of study drug.

Highly effective forms of contraception for females are defined as:

- Combined (estrogen- and progestogen-containing) hormonal contraceptives that inhibit ovulation, including oral, intravaginal, and transdermal products
- Progestogen-only hormonal contraceptives that inhibit ovulation, including oral, injectable, and implantable products
- Intrauterine devices and intrauterine hormone-releasing systems
- Bilateral tubal occlusion (women)
- Male partner vasectomy or other method of surgical sterilization provided that the partner is the sole sexual partner of the study patient and the vasectomized partner has received medical assessment of the surgical success
- Sexual abstinence in men and women (ie, refraining from heterosexual intercourse during the entire period of risk association with the study drugs) when it is the preferred and usual lifestyle of the patient; periodic abstinence (such as calendar, symptothermal, and postovulation methods), withdrawal (coitus interruptus), and the lactational menorrhea method are NOT acceptable methods of contraception.

The following methods of contraception are NOT considered highly effective:

- Progesterone-only oral hormonal contraception that does not inhibit ovulation
- Barrier methods with or without spermicide, or spermicide alone

V4.0_8 Jul 2024 Page 53 of 68

